### **1.2.3. Non-Amgen Non-Investigational Product Background: Moxifloxacin**

Moxifloxacin is a broad-spectrum fluoroquinolone antibiotic that binds to and inhibits the hERG IKr  $\alpha$  subunit and causes a mean increase of the QTc interval of 6 ms after a single 400-mg oral dose. Moxifloxacin is commonly used as a positive control in thorough QT (TQT) studies to satisfy the requirements of ICH E14.

Refer to the regional manufacturer package insert of AVELOX (moxifloxacin hydrochloride) tablets for additional information.

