## 3. INVESTIGATIONAL PLAN

### 3.1. Overall Study Design and Plan

This will be a single-dose and randomized, single-center, 3-period, 3-treatment crossover study in healthy adult subjects to determine whether OM prolongs the QT/QTc interval after a single oral dose administration of 50 mg OM. The total duration of participation in the study will be approximately 55 days, including the screening period. The study will be conducted at a single clinical site.

[figure not shown]
Approved

The overall duration for individual subjects may vary depending on timing of sample shipment and analysis for Part A of the study, to confirm eligibility for Part B.

An overview of the study design is shown in [Figure 1](#).

Approved

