### 3.2. Discussion of Study Design

The purpose of this study is to evaluate the potential for OM to cause QT prolongation. As OM exposure affects cardiac contractility, the primary endpoint for this study will be the QTcF. A supratherapeutic dose of OM is unable to be administered due to the step-wise titration scheme needed to optimize OM dose and safety concerns in healthy subjects. A

crossover design has been selected, with subjects acting as their own controls to minimize inter-subject variability.

This study will be double-blinded for OM and placebo to control for bias in safety assessments, including safety ECGs, and open-label for moxifloxacin as the QTc effects and AEs of this drug are well characterized. The central ECG laboratory and ECG readers will be blinded to treatment sequence, timepoint, and subject.

The anticipated  $C_{max}$  resulting from the 50-mg OM dose used for the assessment of QTc effects will be consistent with that in Phase 3 and will be below 1200 ng/mL. However, to provide further assurance that subjects will not exceed 1200 ng/mL, this study incorporates an initial PK assessment at 25 mg to confirm that individual  $C_{max}$  values do not exceed 350 ng/mL; given the linear PK of OM, a subject with  $C_{max} \leq 350$  ng/mL at 25 mg would be expected to have predicted exposure no higher than 700 ng/mL at 50 mg, and therefore below 1200 ng/mL.

This study will be conducted using healthy subjects to eliminate potential variables known to have an effect on ECG parameters (eg, concomitant drugs, diseases). Subjects will be randomized to treatment in an effort to ensure that baseline characteristics are evenly distributed across treatment sequences. The sample size in this study is driven by the need to perform a by-timepoint statistical analysis of the primary endpoint per the ICH E14 guidance.

Moxifloxacin will be included as a positive control to validate the sensitivity of the assay to detect small increases from baseline in QTc. Following single oral doses of 400 mg moxifloxacin, a QTc increase of 6 ms has occurred at  $t_{max}$ . Moxifloxacin plasma samples will be collected and concentrations may be measured, but PK vs QTc modeling will not be performed, as the QT effects of moxifloxacin are well-known.

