### 3.3. Selection of Doses in the Study

According to ICH E14, the highest therapeutic dose and a supratherapeutic dose are recommended for the QT/QTc study. The OM dose in ongoing Phase 3 studies is individualized using a PK-based titration to avoid excessive OM exposures ( $> 1200$  ng/mL). The observed mean (standard deviation; SD) steady state  $C_{max}$  from a Phase 2 study (20110151) for 25 mg BID and 50 mg BID are 193 (58.5) ng/mL and 492 (115) ng/mL, respectively. A supratherapeutic dose will not be evaluated due to the identified risk of myocardial ischemia or infarction.

Based on Study 20160159, the 25-mg oral solution formulation resulted in a mean (SD)  $C_{max}$  of 220 (71.2) ng/mL after a single dose administration in healthy subjects. This exposure is well below the 1200 ng/mL threshold and the dose is proximal to the 50-mg dose, such that it is anticipated to provide a very reliable prediction of the  $C_{max}$  of 50 mg, given the linear PK of OM.

In Part B, OM treatment will be a 50-mg single dose of oral solution. The 50-mg oral solution dose should achieve therapeutic concentrations (range of 300 to 700 ng/mL). Moxifloxacin 400 mg is associated with an observed 6 ms increase in the mean placebo- and baseline-corrected QTc interval, which is within the range required by ICH.

In summary, to attain clinically relevant concentrations, a single dose of 50 mg oral solution will be administered for the purpose of evaluating the proarrhythmic potential of OM as reflected by change in the QTc interval in healthy subjects.

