## 8. SAMPLE SIZE AND DATA ANALYSIS

### 8.1. Determination of Sample Size

With approximately 60 enrolled subjects, it is estimated that approximately 48 evaluable subjects will have data from all 3 periods in Part B.

Based on the calculation of the sample size for a TQT study, assuming a 1-sided 5% significance level and a within-subject standard deviation (SD) of 7 msec for  $\Delta QTcF$ , and a true mean difference of 3 msec in  $\Delta QTcF$  between OM and placebo, a sample size of 48 evaluable subjects would be expected to provide 99.5% power to demonstrate that the upper bounds of all the 2-sided 90% confidence intervals (CIs) on  $\Delta\Delta QTcF$  will fall below 10 msec for up to 8 timepoints. With the within-subject SD of 8 msec and other similar assumptions, the power will decrease to 96.5%.

Determination of sample size for assay sensitivity:

Assuming a 1-sided 5% significance level and a within-subject SD of 7 msec for  $\Delta QTcF$ , a sample size of 48 evaluable subjects will provide a power of 99.9% to exclude a mean difference of 5 msec in  $\Delta QTcF$  between moxifloxacin and placebo groups from the lower bound of the 2-sided 90% CI on  $\Delta\Delta QTcF$  at at least 1 of the 3 prespecified timepoints. With the within-subject SD of 8 msec and other similar assumptions, the power will decrease to 99%.

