## **6.4** Determination of Sample Size

With approximately 60 enrolled subjects, it is estimated that approximately 48 evaluable subjects will have data from all 3 periods in Part B.

Based on the calculation of the sample size for a TQT study, assuming a 1-sided 5% significance level and a within-subject SD of 7 ms for  $\Delta$ QTcF, and a true mean difference of 3 ms in  $\Delta$ QTcF between OM and placebo, a sample size of 48 evaluable subjects would be expected to provide 99.5% power to demonstrate that the upper bounds of all the 2-sided 90% CIs on  $\Delta\Delta$ QTcF will fall below 10 ms for up to 8 time points. With the within-subject SD of 8 ms and other similar assumptions, the power will decrease to 96.5%.

Determination of sample size for assay sensitivity

Assuming a 1-sided 5% significance level and a within-subject SD of 7 ms for  $\Delta QTcF$ , a sample size of 48 evaluable subjects will provide a power of 99.9% to exclude a mean difference of 5 ms in  $\Delta QTcF$  between moxifloxacin and placebo groups from the lower bound of the 2-sided 90% CI on  $\Delta\Delta QTcF$  at at least 1 of the 3 prespecified time points. With the within-subject SD of 8 ms and other similar assumptions, the power will decrease to 99%.

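### The assay-sensitivity power (99.9% and 99%) names no moxifloxacin effect and cannot be obtained from the 6 ms that the protocol gives elsewhere

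*Protocol*

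**What the plan says.** Protocol 8.1 sets the conditions for the assay-sensitivity calculation: "Assuming a 1-sided 5% significance level and a within-subject SD of 7 msec for" the change from baseline in QTcF. It then claims that "a sample size of 48 evaluable subjects will provide a power of 99.9% to exclude a mean difference of 5 msec", judged by the lower bound of the two-sided 90% CI at one or more of three prespecified timepoints. For the larger SD it adds: "With the within-subject SD of 8 msec and other similar assumptions, the power will decrease to 99" per cent. SAP 6.4 carries the same claim: "a sample size of 48 evaluable subjects will provide a power of 99.9% to exclude a mean difference of 5 ms in" the moxifloxacin-placebo comparison. The paragraph just before it, on primary power, does name its assumed true difference (3 ms). The assay-sensitivity paragraph names none.

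The test itself is in Protocol 8.3.3.4 and SAP 6.1.2. The moxifloxacin-placebo contrast at 2, 3 and 4 h is tested one-sided at 5% against a null of 5 ms or less, with Hochberg control, and one significant timepoint is enough.

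Three sections of the protocol give a moxifloxacin effect, and all give the same one:
- 1.2.3: the drug "causes a mean increase of the QTc interval of 6 ms after a single 400-mg oral dose".
- 3.2: "Following single oral doses of 400 mg moxifloxacin, a QTc increase of 6 ms has occurred at" the time of peak concentration.
- 3.3: "Moxifloxacin 400 mg is associated with an observed 6 ms increase in the mean placebo- and baseline-corrected QTc interval". This is offered as the reason why the control is suitable.

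**The concern.** A true effect of 6 ms lies only 1 ms above the null, while the standard error of the contrast is about 1.4 ms. Power close to 100% is out of reach with those values. Either the calculation used a much larger moxifloxacin effect without saying so, or the printed power does not belong to the planned test.

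The positive control is what allows a negative omecamtiv mecarbil result to be read as absence of effect rather than insensitivity of the study. A reader who wants to know whether 48 evaluable subjects are enough for that purpose gets one near-certain answer from 8.1 and a very different one from the 6 ms in 1.2.3, 3.2 and 3.3. Nothing in the documents shows which one the sponsor relies on.

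**Working it through.** **Inputs.** From Protocol 8.1 and SAP 6.4: n = 48, one-sided alpha 0.05 (critical value 1.645), within-subject SD 7 or 8 ms. From Protocol 8.3.3.4 and SAP 6.1.2: null 5 ms, timepoints 2, 3 and 4 h, Hochberg. From Protocol 1.2.3, 3.2 and 3.3: effect 6 ms. The design is a "single-center, 3-period, 3-treatment crossover study in healthy adult subjects" (Protocol 3.1). The documents give no between-timepoint correlation, so 0 to 0.9 is my assumption. Φ is the standard normal distribution function.

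**Step 1: check the SD convention on the primary power.** Take SE = SD × √(2/48), which is 1.429 ms (SD 7) or 1.633 ms (SD 8). The true difference is 3 ms, the limit 10 ms, and there are 8 timepoints.
- SD 7: 7/1.429 = 4.899; Φ(4.899 − 1.645) = 0.99943; 0.99943^8 = 0.9955. Stated: 99.5%.
- SD 8: 7/1.633 = 4.287; Φ(4.287 − 1.645) = 0.99588; 0.99588^8 = 0.9675. Stated: 96.5%.

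A noncentral t gives 99.4–99.5% and 96.1–96.4%. The plan's primary figures therefore reproduce with this SE. Reading 7 ms as the SD of the paired difference (SE = 7/√48 = 1.010) would put primary power above 99.99%, which does not fit.

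**Step 2: the same formula for moxifloxacin at 6 ms, null 5 ms.**
- One timepoint, SD 7: 1/1.429 = 0.700; Φ(0.700 − 1.645) = 0.172.
- One timepoint, SD 8: 1/1.633 = 0.612; Φ(0.612 − 1.645) = 0.151.
- At least one of three, independent, no multiplicity control: 1 − (1 − 0.1723)^3 = 0.433 (SD 7); 1 − (1 − 0.1509)^3 = 0.388 (SD 8).

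This last case is the most favourable one, because positive correlation and multiplicity control both lower it. The gap to the printed figures is 99.9 − 43.3 = 56.6 points and 99 − 38.8 = 60.2 points. If all 60 subjects were evaluable it would give 47.7% and 42.5%.

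**Step 3: the planned Hochberg test at 6 ms.** Success occurs if the largest p is ≤ 0.05, or the middle one ≤ 0.025, or the smallest ≤ 0.0167. Power was simulated with equally correlated normal statistics, 1,000,000 draws per setting.

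| Correlation | 6 ms at all three: SD 7 / SD 8 | 6 ms at one, 5 ms at the others: SD 7 / SD 8 |
|---|---|---|
| 0 | 22% / 18% | 11% / 10% |
| 0.25 | 20% / 17% | 10% / 9% |
| 0.5 | 18% / 15% | 10% / 9% |
| 0.75 | 15% / 13% | 9% / 8% |
| 0.9 | 14% / 12% | 8% / 7% |

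As a check, Hochberg rejects whenever Bonferroni does. Bonferroni with independent timepoints gives 1 − (1 − 0.0766)^3 = 0.213 (SD 7) and 1 − (1 − 0.0648)^3 = 0.182 (SD 8), so the first row is consistent.

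**Step 4: what effect gives the printed figures?** Solving for 99.9% at SD 7 and 99% at SD 8:
- at least one of three, unadjusted, independent: 9.2 and 9.0 ms;
- at least one of three, alpha/3, independent: 9.9 and 9.8 ms;
- one timepoint, unadjusted: 11.8 and 11.5 ms.

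An effect of 10 ms with alpha/3 and independent timepoints gives 1 − (1 − 0.9148)^3 = 0.9994 (SD 7) and 1 − (1 − 0.8248)^3 = 0.9946 (SD 8); the t version gives 99.9% and 99.3–99.4%. Both printed figures then come out together. Independence matters as well: at 10 ms with Hochberg and correlation 0.5, power is about 99.0% (SD 7) and 96.5% (SD 8).

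**The case against.** The strongest reply is that nothing has been miscalculated. Section 8.1 does not say that power was computed at 6 ms, and both printed figures appear together at about 10 ms. The 6 ms is background: 1.2.3 and 3.2 take it from the product label, and 3.3 uses it to justify the choice of control. No section calls it the expected QTcF effect at 2, 3 and 4 h in this study. The sample size is driven by the primary by-timepoint analysis (Protocol 3.2), whose power reproduces, and the assay-sensitivity rule does not depend on planned power.

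Most of this stands. It rules out calling the arithmetic wrong and leaves the sample size and decision rule untouched. It does not remove the conflict. Section 3.3 describes the 6 ms as placebo- and baseline-corrected, which is the quantity being tested, and no other moxifloxacin effect appears in either document.

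The upper limit of 43% or 39% also depends on the SD convention. With 7 ms read as the SD of the paired difference, the unadjusted figure for at least one of three independent timepoints is about 59%. Step 1 makes that reading implausible, and 59% is still far from 99.9%.

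A reader might also infer that the control is more likely to fail than to pass. That follows only if 6 ms is the true effect in this study, which the documents do not establish. The Hochberg values in Step 3 rest further on an assumed correlation and on how many of the three timepoints carry the full 6 ms.

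**Conclusion.** The concern holds as an undisclosed assumption that contradicts the plan's own figure. The stated 99.9% and 99% cannot be obtained from a 6 ms effect under the documented test and the SD convention confirmed on the primary endpoint. At 6 ms the most favourable case is about 43% (SD 7) or 39% (SD 8). The planned Hochberg test gives about 14–22% or 12–18% if 6 ms holds at all three timepoints, and about 7–11% across both SDs if it holds at only one, with correlation assumed between 0 and 0.9. The printed power needs an effect of about 9 to 10 ms or more, at least 1.5 times the one stated.

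The documents do not support two stronger conclusions: that the calculation is arithmetically wrong, or that 48 evaluable subjects are too few. Both would require knowing that 6 ms was the planning value.

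**What to change.** In Protocol 8.1 and SAP 6.4:
- state the moxifloxacin effect assumed at 2, 3 and 4 h and its basis;
- state the between-timepoint correlation and the multiplicity method behind the power;
- restate the power for the Hochberg test under those assumptions, at SD 7 and SD 8;
- print the power at 6 ms beside it as a sensitivity value, with its assumptions.

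Then reconcile Protocol 1.2.3, 3.2 and 3.3 with the assumed effect. Adding a larger effect to 8.1 alone would leave those three sections in conflict with it.

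The cost is wording only. Sample size, treatments, analysis and decision rule do not change. The one downside for the sponsor is a power figure that is less favourable or openly conditional.

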#### **8.3.3.4. Assay Sensitivity**

The analysis to show assay sensitivity will be based on the change-from-baseline post-dosing QTcF of moxifloxacin. The same model will be used as described for the primary analysis. For the timepoints 2, 3, and 4 hours after dose administration, the contrast in treatment  $\Delta\Delta\text{QTcF}$  = “moxifloxacin – placebo” will be tested against the 1-sided null hypothesis  $\Delta\Delta\text{QTcF} \leq 5$  msec at the 5% level. Multiplicity will be controlled using the Hochberg procedure. If after this procedure QTc ( $\Delta\Delta\text{QTcF}$ ) is significantly larger than 5 msec for at least 1 timepoint, assay sensitivity will be considered shown. In addition, 2-sided 90% CIs will be obtained for the contrast at all timepoints and used in the figures.

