#### 6.1.2 Assay Sensitivity

The analysis to show assay sensitivity will be based on  $\Delta QTcF$  of moxifloxacin. The same model will be used as described for the primary analysis.

For the time points 2, 3, and 4 hours after dose administration, the contrast in treatment  $\Delta\Delta QTcF =$  "moxifloxacin – placebo" will be tested against the 1-sided null hypothesis  $\Delta\Delta QTcF \le 5$  ms at the 5% significance level. Multiplicity will be controlled using the Hochberg procedure. If after this procedure the lower bound of the 2-sided 90% CI for LS mean  $\Delta\Delta QTcF$  is significantly larger than 5 ms for at least 1 time point of these 3 time points, assay sensitivity will be considered shown. In addition, 2-sided 90% CIs will be obtained for the contrast at all time points and used in the figures.

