## 8 Tables, Figures, and Listings

## 8.1 Tables

Number	Title	Comments
14.1.1	Baseline values of ECG parameters with descriptive statistics	Number of subjects (n), mean, SD, 90% CI, median, minimum, and maximum from descriptive analysis will be given by treatment for each ECG parameter (Section 6.1).
14.1.2.1 – 14.1.2.4	Observed values of QTcF, HR, PR, and QRS with descriptive statistics	n, mean, SD, SE, 90% CI, median, minimum, and maximum from descriptive statistics will be given by treatment and postdose time point (Section 6.1).
14.1.3.1- 14.1.3.4	Change-from-baseline QTcF, HR, PR, and QRS (ΔQTcF, ΔHR, ΔPR, and ΔQRS) at each time point	n, LS mean, SE, and 90% CI from the statistical modeling will be given by treatment and time point (Section 6.1).
14.1.4.1- 14.1.4.4	Placebo-corrected change-from- baseline QTcF, HR, PR, and QRS ( $\Delta\Delta$ QTcF, $\Delta\Delta$ HR, $\Delta\Delta$ PR, and $\Delta\Delta$ QRS) at each time point	LS mean, SE, and 90% CI from the statistical modeling will be given by treatment and time point (Section 6.1).
14.1.5	Placebo-corrected change-from- baseline QTcF (ΔΔQTcF) for assay sensitivity test	LS mean, Lower bound of 2-sided 90% CI, P value, and adjusted alpha will be given at each of the 3 prespecified time points (Section 6.1.2).
14.1.6	QTcF outliers per absolute category	Number (%) of subjects and time points with QTcF > $450$ and $\le 480$ ms, $> 480$ and $\le 500$ ms, or $> 500$ ms by treatment (Section 6.2).
14.1.7	QTcF outliers per change-from- baseline category	Number (%) of subjects and time points with $\Delta QTcF > 30$ and $\leq 60$ ms, or $> 60$ ms by treatment (Section 6.2).

Number	Title	Comments
14.1.8	Categorical analyses for HR, PR, and QRS	Number (%) of subjects and time points with $\Delta PR > 25\%$ and $PR > 200$ ms at post-baseline; $\Delta QRS > 25\%$ and $QRS > 120$ ms at post-baseline; $HR$ decrease from baseline $> 25\%$ and $HR < 50$ bpm at post-baseline; and $HR$ increase from baseline $> 25\%$ and $HR > 100$ bpm at post-baseline (Section 6.2).
14.1.9	T-wave morphology and U-wave presence across treatments: treatment-emergent changes	Number (%) of subjects and time points falling into each of the T-wave categories: Normal (+), Flat, Notched (+), Biphasic, Normal (-), Notched (-) as defined in Section 6.2.
14.1.10	Concentration-QTc analysis of OM and associated ΔQTcF prolongation	Fixed-effect estimations and corresponding P values will be given (Section 6.3).

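### SAP 6.1.2 declares assay sensitivity on the 90% CI lower bound, which Hochberg does not adjust; the pass sentence should cite the Hochberg result

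*Protocol*

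**What the plan says.** **Protocol 8.3.3.4.** Moxifloxacin minus placebo is tested at 2, 3 and 4 h against the 1-sided null of at most 5 ms, at 5%. "Multiplicity will be controlled using the Hochberg procedure". The trial passes if the effect itself is significant after that step at one timepoint or more. The intervals have a separate, descriptive job: "In addition, 2-sided 90% CIs will be obtained for the contrast at all timepoints and used in the figures".

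**SAP 6.1.2.** The test and the Hochberg statement are the same, but the pass sentence has a different subject. It begins "If after this procedure the lower bound of the 2-sided 90% CI for LS mean" ΔΔQTcF, and continues "is significantly larger than 5 ms for at least 1 time point of these 3 time points, assay sensitivity will be considered shown".

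**SAP 8.1, Table 14.1.5.** The lower 90% bound is printed next to the P "value, and adjusted alpha will be given at each of the 3 prespecified time points".

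**Protocol 8.1 and SAP 6.4.** With 48 evaluable subjects, power is given as 99.9% (within-subject SD 7 ms) and 99% (SD 8 ms). The powered event is exclusion of a 5 ms difference "between moxifloxacin and placebo groups from the lower bound of the 2-sided 90% CI on" ΔΔQTcF, "at at least 1 of the 3 prespecified timepoints". No multiplicity method and no assumed moxifloxacin effect are given.

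**The concern.** Hochberg compares ordered p-values with 0.05, 0.025 and 0.0167. It leaves a 90% confidence interval as it was. A confidence bound is also not something that can be significantly larger than a constant: it lies above 5 ms or it does not. The only operation that the SAP sentence literally describes is therefore a check of whether any of three unadjusted bounds exceeds 5 ms. That rule does not hold the 5% level over three timepoints.

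A negative QT finding for omecamtiv mecarbil can be interpreted only if the positive control passes. If the bound and the Hochberg result disagree, Table 14.1.5 would show both in one row, and the pass sentence points to the bound.

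**Working it through.** **Inputs.** From the documents: n = 48, SD 7 or 8 ms, threshold 5 ms, 1-sided 5%, three timepoints. Assumed, because the documents do not give them: 94 degrees of freedom, the same true effect at 2, 3 and 4 h, and a correlation between timepoints of 0, 0.5 or 0.8.

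**Standard error.** SE = SD × √(2/48), which is 1.429 ms (SD 7) or 1.633 ms (SD 8).

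**Check on the plan's own figure.** For the OM comparison (true difference 3 ms, margin 10 ms, 8 timepoints), per-timepoint power raised to the eighth power gives 99.5% and 96.4%. The plan states 99.5% and 96.5%. The SE formula with independent timepoints therefore fits how the plan was powered.

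**The two readings.** Order the p-values p1 ≤ p2 ≤ p3.
- Bound reading: pass if p1 < 0.05.
- Hochberg: pass if p3 ≤ 0.05, or p2 ≤ 0.025, or p1 ≤ 0.0167.

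Every Hochberg pass has p1 at or below 0.05, so disagreement runs one way only: the bound passes and Hochberg fails.

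**What a lone timepoint needs.** The t(94) critical values are 1.661 at 0.05 and 2.160 at 0.0167.
- Bound: 5 + 1.661 × SE = 7.37 ms (SD 7) or 7.71 ms (SD 8).
- Hochberg: 5 + 2.160 × SE = 8.09 ms or 8.53 ms.

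**Worked example, SD 7.** LS means of 7.8, 6.5 and 6.0 ms give lower bounds of 5.43, 4.13 and 3.63, so one bound exceeds 5 and the literal sentence passes. The p-values are 0.0265, 0.148 and 0.243. Since 0.243 > 0.05, 0.148 > 0.025 and 0.0265 > 0.0167, Hochberg fails.

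**False-pass rate, all true effects 5 ms** (simulated, correlation 0 / 0.5 / 0.8).
- Bound: about 14 / 12 / 9%. The independent case follows directly: 1 − 0.95³ = 14.3%.
- Hochberg: about 5 / 4.5 / 4%.

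**Chance that the bound passes and Hochberg fails** (simulated, correlation 0 / 0.5 / 0.8).

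| True effect | SD 7 | SD 8 |
|---|---|---|
| 6 ms | 22 / 17 / 13% | 20 / 16 / 12% |
| 7 ms | 23 / 20 / 18% | 25 / 21 / 17% |
| 8 ms | 9 / 13 / 14% | 15 / 17 / 17% |
| 9 ms | 1 / 5 / 7% | 4 / 9 / 10% |
| 9.8 ms | 0.1 / 1 / 3% | 0.7 / 3 / 5% |

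These values can shift by about one percentage point with the way the error variance is simulated.

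**Assay-sensitivity power.** The 99.9% and 99% cannot be rebuilt, because the assumed effect is missing. Solving backwards with independent timepoints:
- The bound reading gives both figures at about 9.1-9.3 ms. At 9.2 ms it gives 99.9% / 99.4%, and Hochberg there gives 99.2% / 96.7%.
- Hochberg gives both figures at about 9.7-10.0 ms. At 9.8 ms it gives 99.9% / 99.2%.
- At 6 ms, the only moxifloxacin effect in the documents (Protocol 1.2.3, 3.2 and 3.3), the bound reading gives about 43% / 39% and Hochberg about 21% / 18%.

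**The case against.** The strongest reply is that there is only one rule. Both documents name Hochberg immediately before the pass sentence, the SAP sentence opens by conditioning on that procedure, and Table 14.1.5 calls for an adjusted alpha, which a bound-only rule would not need. This stands as evidence of intent. A reader might infer that the SAP replaced the protocol's rule with an unadjusted one; the documents do not support that. What the reply does not repair is the sentence itself, which still names a quantity that Hochberg leaves unchanged.

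A second reply is that the power paragraphs give a power basis and not a decision rule. That is correct. A reader might also infer that the power was computed without adjustment, or that it is wrong. Neither is shown, because 99.9% and 99% fit Hochberg near 9.7-10.0 ms as well as the bound near 9.1-9.3 ms. Knowing the effect would not settle it either: at correlation 0.5 the bound reading gives 99.7% / 98.9% at 10 ms, so the effect alone need not identify the rule. The low power at 6 ms shows that a larger effect was assumed. It does not show that the larger effect was unreasonable.

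A third reply is that the size is overstated if only the 14% is quoted. That is fair. The 14% needs independent timepoints and true effects of exactly 5 ms, and timepoints that share each subject's baselines and periods are plausibly correlated. The range of 9-14% is the honest statement.

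**Conclusion.** The point holds as a defect in the decision sentence of SAP 6.1.2. Taken literally, that sentence is an unadjusted test at any of three timepoints. Its false-pass rate is about 9-14% at a true 5 ms, where the stated level is 5% and Hochberg delivers about 4-5%.

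The practical size depends on the true moxifloxacin effect and on the correlation, which are both assumptions here. At about 9-10 ms the two readings disagree in about 0.1-4% of trials at correlation 0, and in up to about 10% at correlation 0.8. At 6-8 ms they disagree in about 9-25%.

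The sample size is not in question: Protocol 3.2 says that it is "driven by the need to perform a by-timepoint statistical analysis of the primary endpoint". The missing moxifloxacin effect is a gap in the power statement and not evidence of an error in it. This should be fixed, because the correction is trivial and a pass that rested only on the bound would be hard to defend after unblinding.

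**What to change.** - **SAP 6.1.2:** replace the pass sentence with: Assay sensitivity is shown if the Hochberg procedure rejects ΔΔQTcF ≤ 5 ms at 1 or more of 2, 3 and 4 h; the 2-sided 90% CIs are descriptive.
- **SAP Table 14.1.5:** base the verdict on the P value against the adjusted alpha. A label marking the 90% bound as unadjusted would help, but is presentation only.
- **Protocol 8.1 and SAP 6.4:** state the assumed moxifloxacin effect, its source, and how it relates to the 6 ms background figure. Confirm that 99.9% and 99% refer to the Hochberg rule, or restate them for that rule.

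The cost is one sentence in SAP 6.1.2, a note to one table, and one sentence in each power paragraph. Sample size, timepoints, threshold, alpha and the Hochberg procedure stay as they are. The only thing given up is the easier reading of the SAP pass sentence.
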